Scientific research and quality initiatives to improve the use of HFrEF medications have primarily focused on healthcare providers.⁹ However, clinical inertia and competing demands on clinician's time are real. Worse, quality metrics and value-based purchasing have not yet created significant "skin in the game" for providers. Providers hold the keys to prescribing yet have little direct incentive to do the hard work of medication optimization.

II.D. Patient-focused approaches require engagement

Existing patient education efforts have focused largely around self-care regarding diet, exercise, and adherence.⁸ Learning techniques are typically passive, most often with printed reading materials. Formal educational initiatives based on these approaches, when tested in randomized trials, have generally been ineffective in improving clinical outcomes.^{12,13} Much less has been done to *engage patients in decisions about medication prescribing*. Given the algorithmic nature of HFrEF treatment regimens and that >80% of Americans with HFrEF have reasonable health literacy,¹⁴ the basic principles of HFrEF medication prescribing are not beyond comprehension of most patients. These principles of medication optimization follow a simple cycle:

- A) identify one HFrEF medicine that is not at goal dose;
- B) initiate the drug or intensify the dose;
- C) monitor for side effects;
- D) repeat approximately every 2 weeks towards recommended maximal doses, as tolerated.

A growing body of evidence suggests that patients are far more likely to understand and adhere to medication regimens that they have participated in creating.^{15,16} Encouraging patient engagement also forces important personalized discussions with clinicians around choices in HFrEF medication prescribing. Finally, patients are more likely to cognitively weigh short-term side effects against the potential of long-term health benefits if they better understand the overall goals of therapy and have participated in prescribing decisions.¹⁷

II.E. A culture of shared decision making facilitates patient engagement in prescribing

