Pilot Outcomes: The primary purpose of the pilot is to assess the feasibility of the study procedures and intervention. Therefore, we will use interview guides and observations to assess the length of study procedures for patients, the logistics of delivering intervention, and the complications that could occur. Through this, we will modify the study procedures accordingly (e.g. understand flow of care at various clinics participating in recruitment, confirm appropriate delivery of the intervention, remove survey measures for excessive length, etc). Please note: Any changes made to the study materials or procedures will be submitted as an amendment and approved by COMIRB before implementation in the main trial.

Trial Primary Outcome: For the trial, the **main measure of effectiveness will be a comparison of the number of HFrEF medication optimizations** (i.e. dose changes for β B, ACEI/ARB/sacubitril, AldA, ivabradine, and hydral-ISDN) between the EPIC-HF intervention arm and usual care arm. This will be assessed through review of medication prescribing at baseline, 1-month following intervention delivery, and 1 year after enrollment.

Trial Secondary Outcomes: A number of additional secondary measures will be collected through patient surveys at baseline and 1-month following intervention delivery, and will be compared between the EPIC-HF intervention and usual care. See Table 1 for survey measures collected.

Table 1.

Surveys to be completed at baseline	Surveys to be completed at follow-up (1 month)
Patient Activation Measure, 13-item (PAM)	Patient Activation Measure, 13-item (PAM)
Patient Assessment of Care for Chronic Conditions Survey (PACIC)	Patient Assessment of Care for Chronic Conditions Survey (PACIC)
Control Preferences Scale (preferred)	Control Preferences Scale (preferred)
REALM-R literacy	Heart Failure History (shortened version)
Heart Failure History	Intervention/Education Use
Subjective Numeracy	
Demographics	

B. Description of Population to be Enrolled:

PATIENTS: For the pilot and the trial, adult patients with HFrEF from UCHealth Metro, North, and South will be enrolled.

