Pilot: For the pilot, we will conduct all trial procedures with a small group of HFrEF patients and clinicians at the 3 main sites (see below for trial details). During this process, we will conduct semi-structured interviews with the patients at baseline and/or post-intervention follow-up to obtain their viewpoints on the study procedures and intervention. Similarly, we will conduct semi-structured interviews with involved clinicians. Clinicians will be identified by study personnel as anyone who treats HFrEF patients and/or had a patient enrolled in the pilot. Clinicians will be recruited over email, phone or in person. Clinician verbal consent will be obtained. Interviews may be audio recorded and transcribed. This will contribute to the feasibility assessment and potential modifications to the trial protocol. Any changes made to study procedures or materials will be submitted to COMIRB for approval prior to use, with the exception of the patient checklist, which will be iteratively developed based off of feedback received from the pilot.

Trial:

Screening: The electronic health record will be queried for eligible patients. Health Data Compass will be used to generate lists of patients for whom LVEF is <=40% or for whom a diagnosis of "systolic heart failure" has been applied in the last year. Cardiology and primary care clinic schedules as well as inpatient cardiology services may be screened to further enrich screening. Patients on these lists will then be screened to confirm the last imaging test shows an LVEF of <=40% and assess upcoming clinic appointments.

Recruitment: We will prospectively enroll patients for this study. Recruitment and consent will be conducted at each site by research personnel. Patients will primarily be recruited in-person during a clinic visit or hospitalization. For some patients, research personnel may call prior to the appointment to see if they would be willing to hear about the study during/after their appointment; these patients will then be consented in person at the appointment. In order to increase representativeness of patients who live in rural areas, and thus may travel to the main study sites for appointments

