infrequently, study personnel have requested a waiver of written consent. Study procedures in their current form require two visits to the study site within one year—this waiver of written consent would allow us to enroll patients for whom traveling to the study site more than once a year might be burdensome or infeasible. In these instances where written consent is not possible to obtain, study personnel will conduct verbal consent with the patient over the phone prior to their clinic appointment at one of the study sites. All in-person consent and enrollment will occur at the clinic or hospital.

Baseline Data Collection: Patients will complete the baseline survey at time of enrollment. Baseline medical record data will also be collected by study personnel.

Randomization: Patients will be randomized to one of two arms:

- ARM 1: a best practices standard care control arm (*control*),
- ARM 2: the EPIC-HF intervention (*engagement tools*)

Randomization will occur using a computer generated system that chooses which of the 2 arms the patient will be put into. This will be used for all participants and tracked by study personnel.

Control and Intervention Activities: Enrolled subjects in the control arm will complete baseline and 1 month post-clinic visit surveys, but will not receive further communications from the study team in order to preserve usual care. Clinicians seeing patients in the control arm have access to multiple heart failure management tools provided through Epic; these will not be modified.

[figure not shown]
Subjects in the EPIC-HF intervention arms will receive intervention materials. These are A) a 3-minute, animated patient-engagement video

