Trial: Basic demographics of the participants will be summarized quantitatively in a way that characterizes the study participants but cannot be traced to individuals.

HFrEF medication dose optimizations (initiations and intensifications) at 1-month and study end will be obtained from the Epic electronic health record and summarized as a count.

Analyses of effectiveness for the primary outcome of dose optimizations will use a repeated measures mixed model. This strategy allows for partially incomplete data (e.g. missing follow-up or one of the patient/caregiver pair) and relaxes missing data assumptions to missing at random conditional on observed data. Prior to these analyses, we will contrast the participants in the arms of the study, identifying any patient/site characteristics that are unbalanced. If more than 3-5 variables are identified, we will develop a propensity score for the likelihood of being in the intervention phase as a secondary analysis. Each analysis model will include an indicator variable for the intervention phase, indicators for each of the sites and the variables identified above.

Quantitative questionnaire data will be scored and summarized according to the methods previously validated and published for each questionnaire. Significance for differences between quantitative statistics will be determined using Chi-square tests.

We will use the following measures:

- Prescribed dose optimizations: Number of initiations and dose intensifications of HFrEF medications.
- Patient Activation Measure: To measure patient activation, we use the 13-item Patient Activation Measure (PAM) developed by Hibbard et al.
- Feasibility: To evaluate feasibility, we will explore participation rates and adherence to the study protocol. Additionally, we will collect information on how the patient and providers perceived the usefulness of the materials, through qualitative interviews conducted during the pilot phase.
- Patient Assessment of Care for Chronic Conditions Survey: Patient perceptions of medical care will be assessed using the Patient Assessment of Care for Chronic Conditions Survey (PACIC) developed by Glasgow et al.
- Control Preferences Scale (preferred): We will measure the participants' preferred role in decision making using the validated Control Preferences Scale.
- Proportion of Days Covered (PDC): Prescription fills compared to the ideal, expressed as a percent of days covered.

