Sample Size: The primary outcome of dose optimizations is used to guide study size. Based on data review from a sample of ambulatory patients with HFrEF seen at University of Colorado Hospital as well as prior work characterizing ambulatory HFrEF care in Denver ([name] K23),¹³ the average number of dose adjustments over a year period is approximately 0.5 (0.6 SD); most dose adjustments occur around the time of hospitalization for decompensation. We assume at least half of patients in the intervention will involve the video and Option Grid in their clinical encounters, and that half of them will experience an average of 1 additional medication optimization. In summary, we surmise that 25% of patients randomized to EPIC-HF realizing additional medication optimization is clinically significant and possible. Assuming a Poisson distribution for the outcome as a count, with a 2-sided alpha of 0.05, a 1-year mortality rate of 15% among ambulatory HFrEF patients,⁵³ and a drop-out rate of 10%, with comparison of each intervention arm to the control, study of 255 patients should allow for reasonable power (>80%) to assess the primary endpoint as well perform hypothesis testing around secondary measures and predetermined subgroup analyses. Due to experiences from other studies of a large dropout rate with this patient population (due to death, withdrawal, and lost to follow-up from severe illness and/or lack of return to UCH medical center for care), we will allot for enrollment of 315 patients.

For the pilot trial, we will enroll no more than 60 patients and clinicians spread between North, South, and Metro/Central.

G. Summarize Knowledge to be Gained:

Pilot: By understanding how a sample of patients engage with and react to the intervention materials, the pilot study will illuminate barriers to implementation of the intervention, as well as any critical flaws with the materials.

Trial: By formally testing, on a multi-site level, the effectiveness of the intervention, we will help inform how best to support patients and providers navigate the complexities of HFrEF prescribing, and whether increased patient engagement around their medication plans leads to improved provider prescribing habits.

H. References:

1. [name] LA, Fonarow GC, Liang L, et al. Medication Initiation Burden Required to Comply With Heart Failure Guideline Recommendations and Hospital Quality Measures. *Circulation*. 2015;132(14):1347-1353.

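### Apart from site, the primary model's covariates are chosen by chance imbalance between randomised arms, with no candidate list and no cut-off, instead of being fixed in advance

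*Combined protocol and SAP*

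**What the plan says.** Section IV.F (Data Analysis Plan, Trial) gives the primary outcome a repeated measures mixed model. The covariates are chosen first: "Prior to these analyses, we will contrast the participants in the arms of the study, identifying any patient/site characteristics that are unbalanced". The result feeds every model: "Each analysis model will include an indicator variable for the intervention phase, indicators for each of the sites and the variables identified above". A secondary analysis depends on the same screen: "If more than 3-5 variables are identified, we will develop a propensity score".

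Only the intervention indicator and the site indicators are therefore fixed. No list of characteristics, test, p-value or standardised-difference threshold appears anywhere in the document.

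Sections IV.C (Randomization) and IV.E describe computer-generated allocation of individual patients to two arms, with no stratification factor stated.

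Elsewhere the document points to baseline variables that could plausibly matter:

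- **Prescribing relative to goal.** Section II.D starts the optimisation cycle with "identify one HFrEF medicine that is not at goal dose". Section II.B says the two main drug classes are prescribed to over 90% of eligible patients but seldom reach optimal doses.
- **Enrolment setting.** Section IV.F (Sample Size) says that "most dose adjustments occur around the time of hospitalization for decompensation", and section IV.C says "Patients will primarily be recruited in-person during a clinic visit or hospitalization".

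The data are largely in hand. Section IV.A says of the primary outcome: "This will be assessed through review of medication prescribing at baseline, 1-month following intervention delivery, and 1 year after enrollment". Section IV.C adds: "Baseline medical record data will also be collected by study personnel".

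**The concern.** In an individually randomised trial, a baseline difference between arms arises by chance. Screening on it selects covariates without regard to whether they predict the outcome. A strong predictor that happens to be balanced is left out, although adjusting for it would still improve precision. An irrelevant variable that happens to differ goes in.

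Because neither the candidates nor the cut-off is stated, the primary model also cannot be written down from the plan. Two analysts could follow section IV.F faithfully and fit different models to the same data. What is at stake is pre-specification of the primary analysis and, depending on the cut-off and the strength of the predictors, some precision.

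**Working it through.** The plan gives no figure for this rule, so there is none to reproduce. The cut-offs below are assumptions, chosen to span common meanings of *unbalanced*. Equal allocation is also assumed.

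**1. Chance that one given baseline variable enters the model.** Inputs: 255 or 315 patients (section IV.F, Sample Size), so n = 127.5 or 157.5 per arm. A p-value rule admits a variable at its own level. For a standardised mean difference (SMD) cut-off c, the probability is 2 × [1 − Φ(c / √(2/n))].

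| Rule | 315 randomised | 255 randomised |
|---|---|---|
| p<0.05 | 5% | 5% |
| p<0.10 | 10% | 10% |
| SMD>0.2 | 7.6% | 11.0% |
| SMD>0.1 | 37% | 42% |

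Example: 0.1 / √(2/157.5) = 0.887, and 2 × [1 − Φ(0.887)] = 0.375.

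**2. Chance that two rules pick different covariate sets.** Take 10 independent candidates (assumed). At these sample sizes the rules are nested, so the probability is 1 − [1 − (p₂ − p₁)]¹⁰.

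- p<0.05 against SMD>0.1: 1 − (1 − 0.325)¹⁰ = 98% with 315 patients; 1 − (1 − 0.375)¹⁰ = 99% with 255.
- p<0.05 against p<0.10: 1 − 0.95¹⁰ = 40%.
- p<0.05 against SMD>0.2: 1 − (1 − 0.026)¹⁰ = 23% with 315; 1 − (1 − 0.060)¹⁰ = 46% with 255.

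**3. Propensity-score trigger.** With 10 independent candidates and 315 patients, the binomial chance that more than 3 are flagged is 0.1% at p<0.05 and 55% at SMD>0.1. Whether the secondary analysis happens depends on the same missing definition.

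**4. Type I error.** Simulation used ordinary least squares on a single outcome with site indicators and 10 independent normal covariates, which simplifies the planned mixed model. With no true effect, rejection rates were 3.5-5.3% for the p<0.05 rule, 2.9-5.3% for SMD>0.1 and 4.4-5.6% for a fixed list of two covariates. Rejection reached 6.0-7.9% only when the best of five cut-offs was taken after seeing results.

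**5. Power.** Inputs from section IV.F (Sample Size): a gain of 0.25 on a mean of 0.5, SD 0.6, Poisson count, 15% mortality and 10% drop-out. Analysed per arm: 315 × 0.75 / 2 = 118. Effect: 0.25/0.6 = 0.417 SD, or 0.25/√0.625 = 0.316 SD using the average Poisson variance (0.50 + 0.75)/2. R² is not in the documents. At an assumed joint R² of 0.25:

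| Effect | No covariates | p<0.05 rule | SMD>0.1 rule | Fixed list of two |
|---|---|---|---|---|
| 0.316 SD | 67-68% | 68% | 72% | 70-76% |
| 0.417 SD | 89% | 90% | 93% | 90-95% |

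The low end of the last column has the two listed covariates no stronger than the other eight; the high end has them carrying 80% of R². Across all settings, including 96 analysed per arm (255 × 0.75 / 2), the list differed from each rule by these percentage points:

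| Assumed R² | Against p<0.05 rule | Against SMD>0.1 rule |
|---|---|---|
| 0.09 | −1 to +3 | −1 to +3 |
| 0.25 | +1 to +10 | −3 to +5 |
| 0.36 | +1 to +14 | −6 to +7 |

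**6. Verdicts.** With a true effect, the p<0.05 and SMD>0.1 rules disagreed about significance at 0.05 in 4-18% of trials over R² 0.09 to 0.36. Closer pairs (p<0.05 against p<0.10 or SMD>0.2) disagreed in about 3-8%. With no effect, the wide pair disagreed in 2-3%.

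**The case against.** The strongest reply is that the plan places the comparison before the analyses, always adjusts for site, and loses nothing in validity: a fixed imbalance rule holds its type I error. That stands. A reader might infer that the rule biases the effect or inflates false positives. The documents do not support this, because inflation needs a cut-off chosen after results, and the stated order does not provide for that. But stating the order of steps does not say which variables are checked or what counts as unbalanced.

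Further objections are partly right:

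- **Different models.** It is tempting to say that any two readings would almost always give different models. That is true of the widest pair in step 2, not of closer ones.
- **Power.** The stated variance, 0.6² = 0.36, is below the stated mean of 0.5. If counts were Poisson given covariates, total variance could not be below the mean, so these figures leave no room for variance explained by covariates. No R² can be derived from them. At R² 0.09 the gain is close to simulation noise, and a weak list can lose to a loose SMD rule.
- **Predictors.** The plan does not itself identify baseline predictors. Section II.D is background on titration. The hospitalisation remark concerns when adjustments occur, not whether patients enrolled in hospital later have more of them. *Plausible* is as far as the text goes.
- **Unit of screening.** Section IV.A lists five drug groups. If they are screened separately and independently, at least one is flagged in 1 − 0.95⁵ = 23% of trials at p<0.05 and in 1 − 0.625⁵ = 90% (315 patients) at SMD>0.1. The entry rates in step 1 treat baseline prescribing as one variable.

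Defining *unbalanced* and the candidates would cure the ambiguity, but would still select covariates on chance differences.

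**Conclusion.** The concern holds as a gap in pre-specification of the primary model, and it should be fixed before any comparison by arm. Apart from site, covariates enter according to chance imbalance judged by an unstated standard. A given plausible predictor enters in 5% of trials at p<0.05 and in 37-42% at SMD>0.1. The selected set differs between two reasonable readings in 23% to 99% of trials, depending on the pair. These figures rest on assumed cut-offs, equal allocation and, for the sets, 10 independent candidates; they need no outcome assumption.

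The effect on power is conditional: about nil to 3 points at R² 0.09, more if the listed covariates are strong, and possibly a loss against a loose SMD rule if they are weak. The case for the change rests on pre-specification, not on a promised gain.

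The wording about an intervention phase, and the phased roll-out sentence in section IV.E, might suggest a stepped design in which imbalance would be systematic. The randomisation described in section IV.C, and section IV.E's own account of patient-level randomisation, do not support that reading. The roll-out sentence needs reconciling with them.

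**What to change.** Replace the imbalance rule in section IV.F with: *The primary model will include randomised arm, site, and a short list of baseline covariates fixed before any comparison by arm. The list will include baseline HFrEF prescribing (a defined measure that reflects dose relative to goal as well as classes prescribed, taken from the baseline prescribing review) and, if the investigators judge it prognostic, enrolment during a hospitalisation (yes/no).*

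- A count of classes alone would not serve well. Section II.B puts the gap in the main classes at dose rather than prescription.
- Keep the baseline comparison as description, or use imbalance-selected covariates only in a labelled sensitivity analysis.
- Do not adjust for hospitalisation during follow-up, which occurs after randomisation.
- Write *arm* for *intervention phase*, and reconcile the phased roll-out sentence in section IV.E with the randomisation in section IV.C.
- Optionally, drop the secondary propensity-score analysis, or give its trigger as one number with a defined cut-off; a range of 3-5 is not a single threshold.

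Cost: wording, an early commitment to the list, and one baseline prescribing measure to define. Prescribing at baseline is already reviewed and baseline record data are already collected; enrolment setting is at most one yes/no field. Design, visits and sample size do not change. The downside is little or no power gain if the chosen covariates prove weak.

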COMIRB Protocol

COLORADO MULTIPLE INSTITUTIONAL REVIEW BOARD
[name] [contact] [contact]

Protocol #: 17-1249

Project Title: A clinical trial of an Electronic health record-leveraged, Patient-centered, Intensification of Chronic care for Heart Failure (EPIC-HF) patient engagement video and medication options checklist

Principal Investigator: [name]., MHS

Version Date: 06/14/2018

I. Hypotheses and Specific Aims:

Aim I: Pilot test the screening, enrollment, intervention, and data collection to be used in the Electronic health record-leveraged, Patient-centered, Intensification of Chronic care for Heart Failure (EPIC-HF) trial.

- *Hypothesis 1:* Pilot testing of the feasibility and acceptability of study procedures—using survey tools and qualitative interviews—will lead to important modifications prior to conduct of the full trial.

Aim II: Assess the effectiveness of a pre-clinic patient activation video and in-clinic medications checklist to improve medication prescribing for patients with heart failure with reduced ejection fraction (HFrEF), the EPIC-HF intervention.

- *Hypothesis 1:* Compared to usual care, EPIC-HF will increase the number of HFrEF medication optimizations, without compromising secondary outcomes, including safety and healthcare provider satisfaction.
- *Hypothesis 2:* Compared to usual care, EPIC-HF will increase participant activation, control preferences, and adherence to their HFrEF medication regimen.

II. Background and Significance:

II.A. HFrEF treatment regimens are increasingly complex

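### The only test named for the questionnaire scores is chi-square, with no categories defined and no use of the baseline scores collected, so for PAM and PACIC it is either undefined or wasteful.

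*Combined protocol and SAP*

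**What the plan says.** Section IV.F (Data Analysis Plan, Trial) deals with the questionnaires in two consecutive sentences. The first is "Quantitative questionnaire data will be scored and summarized according to the methods previously validated and published for each questionnaire". The second is "Significance for differences between quantitative statistics will be determined using Chi-square tests". No other test is named for a questionnaire outcome.

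The model described just before is tied to a different outcome: "Analyses of effectiveness for the primary outcome of dose optimizations will use a repeated measures mixed model".

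Section IV.A says of the secondary outcomes: "A number of additional secondary measures will be collected through patient surveys at baseline and 1-month following intervention delivery". Table 1 lists PAM, PACIC and the Control Preferences Scale at both times. Aim II, Hypothesis 2 is that, compared with usual care, "EPIC-HF will increase participant activation, control preferences, and adherence to their HFrEF medication regimen".

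The Sample Size paragraph says "study of 255 patients should allow for reasonable power (>80%) to assess the primary endpoint as well perform hypothesis testing around secondary measures". It gives no effect size, SD or power for any secondary measure.

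**The concern.** PAM and PACIC yield scores, and the plan itself calls the statistics quantitative. Pearson's chi-square has no meaning for a score until the score is cut into categories. No cut-point, level or responder definition appears anywhere in the document, so two analysts following the plan could run different tests.

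Whatever the categories, a table of arm by category at 1 month does not use the baseline score, although it is collected on the same instrument.

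At stake is the sensitivity of the secondary comparisons. Activation is the one that matters most, because it is in Hypothesis 2. PACIC is a Table 1 measure that Hypothesis 2 does not name. The trial could miss a real change in activation that its own data would have shown under an ordinary analysis of the scores.

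**Working it through.** **The plan's own figure.** There is none to reproduce. The power statement of more than 80% with 255 patients belongs to the primary endpoint. What follows is a comparison of methods under stated assumptions.

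**Inputs from the Sample Size paragraph.** Two-sided alpha 0.05; 255 patients, with enrolment up to 315; 15% one-year mortality; 10% drop-out.

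**Assumptions.** Normal scores with equal SD, 1:1 allocation (the ratio is not stated), a true difference d of 0.35 or 0.25 SD, and a baseline to 1-month correlation ρ of 0.3 to 0.7.

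**Analysed per arm (n).**
- 255 × 0.75 / 2 = 95.6, about 96
- 315 × 0.75 / 2 = 118.1, about 118
- 315 × 0.90 / 2 = 141.8, about 142. This applies drop-out only, since the survey is at about 1 month.
- 255 × 0.90 / 2 = 114.8, about 115, which lies inside the 96 to 118 range

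**Formulas, with d = 0.35.**
- *Median split.* The proportions above the cut are Φ(−0.175) = 0.431 and Φ(0.175) = 0.569, a difference of 0.139. Noncentrality λ = 2n × 0.139², which is 3.71, 4.55 and 5.48 for n = 96, 118 and 142, on 1 df.
- *Four equal levels.* λ = (n/2) Σ(p − q)²/p̄, where p and q are the category proportions in the two arms and p̄ is their mean. With control proportions 0.309, 0.261, 0.233 and 0.198, reversed in the intervention arm, λ = 4.97, 6.11 and 7.35, on 3 df.
- *t-test.* δ = d√(n/2) = 2.42, 2.69 and 2.95.
- *ANCOVA.* δ/√(1 − ρ²). At n = 96 this is 2.54 for ρ = 0.3 and 3.40 for ρ = 0.7.

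**Power at d = 0.35.**

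| Test | n = 96 | n = 118 | n = 142 |
|---|---|---|---|
| Chi-square, median split | 49% | 57% | 65% |
| Chi-square, four levels | 44% | 53% | 61% |
| t-test, unadjusted | 68% | 76% | 84% |
| ANCOVA, ρ = 0.3 to 0.7 | 72–92% | 80–96% | 87–98% |

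Simulation (10,000 runs per cell, bivariate normal) agrees within about 4 points. The largest gaps are for the median split (52–53%, 57–58% and 62–63%), where discreteness matters.

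**Power at d = 0.25, n = 96 to 118 (simulated).** Median split 31–35%, four levels 24–30%, t-test 40–49%, ANCOVA 44–77%.

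**The two losses separately, at d = 0.35.**
- *Cutting at the median* costs 68 − 49, 76 − 57 and 84 − 65, which is 19 points each time (14 to 21 in simulation).
- *Adjusting for baseline* adds 3 to 4 points at ρ = 0.3 (72 − 68, 80 − 76, 87 − 84) and 14 to 24 points at ρ = 0.7 (98 − 84 up to 92 − 68).

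**Efficiency.** A median split has large-sample efficiency 2/π = 0.64 relative to the comparison of means, so 96 per arm act like 61, and 118 like 75.

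**Type I error (simulated, d = 0).** Median split 0.040–0.065, four levels 0.049–0.053, t-test 0.043–0.053, ANCOVA 0.047–0.053. With a fixed cut rule there is no material inflation, though the median split strays from 5% because it is discrete.

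**The case against.** The strongest reply is that the plan is ambiguous rather than wrong. The chi-square sentence names neither PAM nor PACIC. The published scoring methods it adopts may define categories. The term could also loosely cover a rank or trend test referred to a chi-square distribution. That last reading matters for size. In simulation at d = 0.35 and 96, 118 and 142 per arm, a Kruskal-Wallis test on uncut scores has 65%, 74% and 82% power, and a four-level linear trend test has 59%, 70% and 77%. The loss against a t-test therefore runs from about 2 to about 23 points, depending on a choice the plan leaves open.

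Part of this stands. The size of the loss depends on the test, and the figures should be read as illustrative. It is also true that one-year mortality is a harsh deduction for a 1-month survey, and that no power target is promised for secondary outcomes.

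The rest does not remove the problem:
- The published methods are invoked for scoring and summarising, not for defining test categories.
- A rank or trend test is not what is written, and neither uses the baseline score.
- The covariate sentence about each analysis model lists phase, site and unbalanced characteristics. A baseline score would enter only if it happened to be unbalanced, and a plain chi-square test takes no covariates.
- Having to guess among these readings is itself the defect.

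**Conclusion.** The concern holds. As written, the test for PAM and PACIC either cannot be run or discards information. On the plain reading, at an assumed 0.35 SD, categorising costs about 14 to 23 points of power against an unadjusted comparison of scores. Ignoring baseline forgoes a further 3 to 24 points. The sizes rest on the assumed effect, correlation, normality and 1:1 allocation. The direction was the same at every value tried.

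The harm is limited to secondary outcomes. The primary analysis is untouched and, for a cut rule fixed in advance, false positives are not the issue. Cut-points chosen after seeing the data would not have that protection. This should be fixed, but it does not threaten the trial's main result.

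Two side points do not carry the finding. For the Control Preferences Scale, chi-square is defensible if the preferred role is treated as nominal, though order and baseline are ignored. Proportion of Days Covered comes from pharmacy fills, is not clearly covered by the chi-square sentence and has no clearly assigned test, although adherence is in Hypothesis 2.

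**What to change.** Replace the chi-square sentence with wording such as: *PAM and PACIC scores at 1 month will be compared by linear regression (ANCOVA) on randomised arm, baseline score and site, reporting the adjusted difference and 95% confidence interval. The Control Preferences Scale will be analysed by ordinal logistic regression adjusted for baseline category. Chi-square is reserved for nominal variables.* If the authors prefer to treat the Control Preferences Scale as nominal, chi-square can stay for it, but the plan should commit to one choice.

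If a categorised PAM or PACIC analysis is also wanted, state the categories before analysis. Add one line on how participants with a missing baseline score are handled. Separately, name a method for Proportion of Days Covered that suits a bounded percentage, for example linear regression on arm and site with robust standard errors.

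The cost is a few lines of analysis text. Baseline PAM and PACIC are already collected, so no new data are needed.
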